## 4.3 As-Treated Analyses

Patients who choose a treatment arm upon enrollment may ultimately be treated as intended or may have first received treatment of the other arm, or treatment may be delayed or postponed. For as-treated analyses, we will classify participants' treatment arm according to the first treatment observed within six months of enrollment (BST, radical cystectomy, or none observed within six months). Patients with no bladder cancer treatment observed within six months will be excluded from as-treated analyses directly comparing BST to radical cystectomy. Outcomes and characteristics of patients with no treatment observed will be presented and informally compared to the as-treated groups. The statistical

approach with the as-treated groups will otherwise mimic ITT analyses. Results from the ITT analysis will be considered primary, with as-treated analyses considered secondary.

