## 1.4 Enrollment Timing

A participant's study clock begins on the date of completion of the baseline survey entry date.

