## 4.2 Secondary Outcomes

Other patient reported outcomes will be evaluated using a similar analytic framework to the primary outcome. To test the hypothesis that cancer-specific survival will be better in patients undergoing radical cystectomy, we will use a superiority testing framework. For assessment of time-to-event outcomes we will use inverse probability weighted Cox proportional hazards models to estimate relative risks. Survival outcomes will be censored at the time of the last study contact or clinic visit for patients who are lost to follow-up and have no recent EHR-verified clinic visits. Since time-to-event outcomes (cancer-specific survival and metastasis-free survival) will be highly correlated with one another, two-sided 95% confidence intervals will be used for inference without adjustment for multiple survival endpoints.

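### The as-treated survival analyses count the wait for treatment as treated follow-up, which tilts the cancer-specific hazard ratio toward the arm that waits longer if waits differ and cancer deaths precede treatment

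*SAP*

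**What the plan says.** SAP 1.4 defines a single time origin: a participant's "study clock begins on the date of completion of the baseline survey entry date". SAP 4.3 then classifies each patient for the as-treated analyses "according to the first treatment observed within six months of enrollment (BST, radical cystectomy, or none observed within six months". It adds: "Patients with no bladder cancer treatment observed within six months will be excluded from as-treated analyses directly comparing BST to radical cystectomy". It recognizes that a patient may cross to the other treatment first, "or treatment may be delayed or postponed".

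On method, SAP 4.3 says only that the statistical "approach with the as-treated groups will otherwise mimic ITT analyses". For survival, the intention-to-treat (ITT) method is in SAP 4.2: "For assessment of time-to-event outcomes we will use inverse probability weighted Cox proportional hazards models to estimate relative risks". Neither section names a different time origin, a delayed-entry rule, a landmark or a time-varying treatment for the as-treated version. SAP 4.3 does not mention survival outcomes by name, but it does not exempt them.

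Two statements limit the reach of the point: "Results from the ITT analysis will be considered primary, with as-treated analyses considered secondary", and "Outcomes and characteristics of patients with no treatment observed will be presented and informally compared to the as-treated groups".

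**The concern.** The arm is determined by something that happens after the clock starts. To be counted in either as-treated arm, a patient must live long enough to be treated. The interval from baseline survey to first treatment therefore cannot contain a death, yet it is counted as time at risk in the arm eventually joined. This is immortal-time bias. Inverse probability weights built from baseline covariates do not remove it, because arm membership depends on survival after baseline.

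If both arms wait equally long, the effect cancels. If one arm waits longer, and there is a real hazard of cancer death during the wait, the hazard ratio favors that arm. If cystectomy is the slower treatment to start, the bias runs toward the hypothesis in SAP 4.2 that cancer-specific survival is better with cystectomy.

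The as-treated analysis is there to show whether treatment received tells a different story from treatment chosen. Part of any gap between the as-treated and ITT ratios could be waiting time rather than treatment.

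**Working it through.** **The plan's own figure.** The documents give no figure for the as-treated analysis. The nearest is the power in SAP 6 for 1-year bladder cancer mortality of 4.8% against 1%, stated as above 80%. With 337 and 235 patients (Protocol 9.4), two-sided alpha 0.05 and unpooled variance:

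- SE = √(0.01×0.99/235 + 0.048×0.952/337) = 0.0133
- power = Φ(0.038/0.0133 − 1.96) = Φ(0.89) = 81.3%

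This reproduces the statement at the full 572. The same risks and arm sizes are used below.

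**Inputs from the documents.** 235 cystectomy (RC) and 337 bladder-sparing (BST) patients; 12-month cancer death risks of 1% and 4.8% (SAP 6) or 0.8% and 3.6% (Protocol 9.4); the six-month window (SAP 4.3).

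**Assumptions.** Waits are gamma distributed with shape 2. Mean wait is 0.75 month for BST and 1.5, 2 or 3 months for RC. Patients are kept if treated within six months and alive at treatment. No weighting and no crossover.

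**Hand approximation.** Under constant hazard, a kept patient has no hazard during the wait and the usual hazard afterwards. Over 12 months the ratio is therefore multiplied by about

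(12 − mean RC wait) / (12 − mean BST wait),

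with means taken among those treated within six months. For a gamma wait with shape 2 and mean m, that mean is m × P(Gamma₃ ≤ 12/m) / P(Gamma₂ ≤ 12/m). For m = 2 it is 2 × (1 − 25e⁻⁶)/(1 − 7e⁻⁶) = 1.909. For m = 1.5 and 3 it is 1.484 and 2.516; for BST it stays at 0.750. The factors are:

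- 10.516/11.25 = 0.935
- 10.091/11.25 = 0.897
- 9.484/11.25 = 0.843

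**Cox model.** Solving the large-sample Cox score equation numerically gives the table below. Bias is in standard errors (SE) of the log hazard ratio.

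| Scenario, 12 months | True HR | RC wait 1.5 | RC wait 2 | RC wait 3 | Bias, SE |
|---|---|---|---|---|---|
| 4.8% in both arms, constant hazard | 1.00 | 0.934 | 0.895 | 0.841 | 0.17, 0.26, 0.40 |
| 4.8% in both arms, low early hazard (Weibull shape 2) | 1.00 | 0.983 | 0.969 | 0.946 | 0.04 to 0.14 |
| SAP risks 1% / 4.8%, constant hazard | 0.204 | 0.191 | 0.183 | 0.172 | 0.09, 0.14, 0.21 |
| SAP risks, low early hazard | 0.204 | 0.201 | 0.198 | 0.193 | 0.02, 0.04, 0.07 |
| Protocol risks 0.8% / 3.6%, constant hazard | 0.219 | 0.205 | 0.196 | 0.185 | 0.08, 0.13, 0.19 |

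The true ratios are ln(0.99)/ln(0.952) = 0.204 and ln(0.992)/ln(0.964) = 0.219. The hand factor reproduces the planned-risk row, for example 0.204 × 0.843 = 0.172.

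**Other cases.**

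- Equal waits: 1.000.
- Reversed waits (RC 0.75; BST 1.5, 2, 3), null, constant hazard: 1.071, 1.117, 1.189.
- 48 months, null: 0.983, 0.973, 0.959 with constant hazard; 1.00 to two decimals with low early hazard.
- Expected RC deaths before treatment within six months: 1.4, 1.9, 2.7 at 4.8%; 0.3, 0.4, 0.6 at 1%.

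**Does the remedy work?** With risk time started at first treatment, the same model returns the true ratio in every case, reversed waits included. A separate simulation of 6 million patients per scenario, with gamma shape 4 and mean waits of 2 vs 1 and 3 vs 1 months, gave 0.91 and 0.83 under the SAP rule (null, 4.8%, 12 months). Reversing to 1 vs 2 months gave 1.10. Delayed entry or a six-month landmark gave 0.99 to 1.01 at 12 months.

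**The case against.** The strongest reply concerns materiality. The analysis is secondary and ITT is untouched. Neither the size nor the direction of the bias can be fixed, because the documents give no waits by arm. The larger figures need a 3-month cystectomy wait, no treatment effect, 12 months of follow-up and a full cancer-death hazard from the first day. That last assumption is doubtful in patients with Tis, Ta or T1 disease and no prior muscle-invasive or metastatic cancer (Protocol 5.4.1 and 5.4.2). With low early hazard at the SAP's planned risks the bias is at most 0.07 SE. Even at 0.84 the two-sided type I error rises only from 5.0% to Φ(−1.56) + Φ(−2.36) = 6.8%. All of that stands.

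It can also be said that the criticism rests on silence, since SAP 4.3 gives no time origin. This carries less weight. There is one clock, one survival model and an instruction to follow the ITT approach, so an analyst following the text would start follow-up at the baseline survey. Presenting the outcomes of untreated patients makes the excluded deaths visible but does not correct the ratio.

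Finally, delayed entry has a cost: it conditions on reaching treatment event-free, and delay may itself reflect disease course. That is a reason to report pre-treatment events alongside it, not to count waiting time that cannot contain a death.

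**Conclusion.** The concern holds. Followed as written, SAP 4.3 gives an as-treated cancer-specific hazard ratio biased toward the arm with the longer wait, whenever waits differ and there is a real hazard of cancer death before treatment. Under the assumed waits with cystectomy slower, the bias is at most 0.40 SE with no true effect and 0.02 to 0.21 SE at the SAP's planned risks. It shrinks with longer follow-up, vanishes with equal waits and reverses if BST waits longer. These sizes rest on assumed gamma waits and an unweighted model without crossover, and they concern cancer-specific death only.

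The bias would not by itself change a conclusion, and the ITT survival result is not affected. It is nevertheless systematic, so a larger sample would not remove it, and it falls on the contrast that the as-treated analysis is meant to inform. The change should be made. Confidence is medium, because the actual waits are unknown.

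**What to change.** In SAP 4.3, for time-to-event outcomes:

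- Keep the enrollment clock, but let each patient enter the as-treated risk set only at the date of first treatment, and only if event-free then. Under the same rule, a patient with a metastasis before first treatment does not enter the as-treated metastasis-free survival comparison.
- Report pre-treatment events and time to first treatment by chosen arm.
- Optionally add a six-month landmark analysis as a sensitivity check.
- Leave the ITT analysis on the enrollment clock.

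The cost is a few lines of SAP text and an entry time in the Cox model. The first-treatment date is already needed to classify patients, and treatments are abstracted from the medical record (Protocol 6.6). The price is that pre-treatment events leave the as-treated ratio, which is why they should be reported separately. The change would follow the March 14, 2024 data freeze (SAP 1.6), so it should be made before the final refresh, estimated for January 2025, and labelled as made after the first freeze.

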#### 4.4 Sensitivity Analyses

As a complementary sensitivity analysis to the primary analytic approach of TMLE, we will use alternative approaches such as propensity score matching and G-computation methods to deal with potential treatment selection bias. Any potential differences in results would be investigated and substantive departures from the TMLE results will be reported. We will also use generalized estimating equations with robust standard errors as a secondary approach towards analyzing longitudinal patient reported outcomes. For patients that die, in sensitivity analyses we will impute the floor of each QOL instrument for all subsequent time points to provide death-adjusted treatment effect estimates.

Despite our intent to be comprehensive in identifying important variables that we can measure in comparing BST and radical cystectomy, it remains possible that unknown unmeasured confounders may remain. For example, beyond collecting tumor stage classification, histology, multifocality, and tumor size, there may be residual cancer severity characteristics that are difficult to extract from health record data. For binary or time-to-event endpoints, we will calculate E-values to evaluate the minimum strength of association an unmeasured confounder would need to have to fully explain away any observed treatment effect.

### 5. Compliance, Retention, and Missing Data

#### 5.1 Adherence and Retention

Participant follow-up assessments are completed in-person, online, by phone, or by mail. Study staff from the University of Washington Clinical Coordinating Center will contact the participant to complete the follow-up assessments. Outreach will include a combination of phone, mail, and email as determined by the contact information provided by the participant. If the contact protocol is exhausted and the assessment has not been completed, a research coordinator at the participant's enrollment site will be notified. Research personnel will review the EMR and provide any site-specific or EMR-specific updates that may be helpful, for example, updating a telephone number. Additional contact attempts (calls, emails, texts, etc.) may be attempted from the local site coordinators.

Participants may experience research assessment burnout due to the frequency and number of questions asked of them. To optimize complete data collection, research personnel may instead complete a subset of survey responses (minimal research assessment). If a participant requests to complete a minimal research assessment, research personnel will prioritize asking research participants the primary and secondary outcome measures.

#### 5.2 Missing Data and Dropouts

We will strive to sustain excellent participant involvement throughout the study, and we have achieved 90%+ follow-up rates in numerous prior studies. The Data Coordinating Center at the University of Washington will generate automated nightly reports, available to staff at the study sites, identifying these fields with a request to discuss and prevent further missingness. Important data elements will be prospectively monitored to examine patterns of missingness.

### 5.3 Handling

In final manuscripts and analyses, the number of non-responders will be enumerated by study arm according to CONSORT guidelines. We will conduct a missing data analysis to describe and characterize enrolled participants who do not provide further response due to *attrition* or *dropout*. As a part of treatment effect estimation, the TMLE algorithm provides an integrated approach to incorporating uncertainty that arises due to missing longitudinal data. The mean outcome conditional on observing the outcome may be a biased estimate when missingness is informative. TMLE can reduce this bias when missingness is a function of measured baseline demographic and clinical characteristics. Missing outcome measurements will be accounted for by nonparametrically estimating the missing data mechanism to produce a matrix of missing data probabilities conditioned on baseline demographic and clinical characteristics. The missing data conditional probabilities will then be incorporated into the TMLE estimation procedure during the third step of updating potential outcomes.

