treatment effect of radical cystectomy through the creation of *potential outcomes*: two predicted outcomes for each individual patient participant, under the hypothetical assumption that they had been treated with either radical cystectomy or medical management. Next, similar to a propensity score approach, TMLE estimates the probability of treatment with radical cystectomy using either logistic regression, machine learning (LASSO, regression trees, etc.) or super learning approaches.¹⁶ In the third step of the TMLE approach, we use the probabilities obtained in the second step to update the initial estimate of each patient participant's pair of potential outcomes under each treatment group. Specifically, we will generate *targeted* estimates of the potential outcomes with regression models that incorporate both the initial potential outcome estimates and the probability of being treated with radical cystectomy. The average treatment effect is the mean difference between the updated potential outcomes and is interpreted as the causal difference in QOL if all patients had been treated with medical management versus having been treated with radical cystectomy.¹⁶ Because each patient has a pair of potential outcomes under each treatment, subgroup analyses are straightforward. As a secondary sensitivity analysis, we will evaluate these data using propensity score and G-computation methods. As a doubly robust and more efficient analytic approach relative to the comparative secondary approaches, we will use TMLE for presentation of the primary results for this study.

Longitudinal trajectories of the effect of treatment on patient QOL over time will be modeled and characterized using standard linear mixed effects models (primary analysis) or generalized estimating equations (GEE, secondary analysis). We will include covariates in the longitudinal data model to provide treatment effect estimates for subgroups of interest such as those defined by age, comorbidity, caregiver status, tumor severity, and use of investigational agents. For assessment of time-to-event outcomes (e.g., survival), we will use an extension of the TMLE approach appropriate for survival data.¹⁷

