9.3 Missing Data

The CISTO research team aims to maintain the highest level of participant involvement and survey completion; they have achieved over 90% completion rates over similar time periods in a prior study with a similar data collection burden.¹¹ Because missing data is always a possibility, the DCC will monitor missing data through automated nightly reports, making these available to staff at CISTO practice sites to correct missing data fields, if possible. These reports will also be used to create a plan to prevent missing data in the future a participant or practice site which previously provided incomplete data. Important data elements will be prospectively monitored to examine patterns or reasons for “missingness”.

As a part of treatment effect estimation, the TMLE algorithm provides an integrated approach to incorporating uncertainty that arises due to missing longitudinal data. The mean outcome conditional on observing the outcome may be a biased estimate when missingness is informative. TMLE can reduce this bias when missingness is a function of measured baseline demographic and clinical characteristics. Missing outcome measurements will be accounted for by nonparametrically estimating the missing data mechanism to produce a matrix of missing data probabilities conditioned on baseline demographic and clinical characteristics. The missing data conditional probabilities will then be incorporated into the TMLE estimation procedure during the third step of updating potential outcomes.¹³

When missing data are suspected to be *missing not at random*, any standard analysis of the available cases is likely biased. The bias cannot be corrected since missingness depends on unobserved data and therefore cannot be empirically modelled reliably. We will therefore assess the sensitivity of inferences made from missing data by imputing missing data under both pessimistic and optimistic scenarios and repeating the TMLE algorithm to provide bounds on the statistical uncertainty. The characteristics of non-responders will be summarized in our final report and we will present the heterogeneity of the treatment effect due to missing data.

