## 2. Primary Outcome

The *primary outcome* is patient-reported health-related quality of life as measured with the EORTC QLQ-C30, which has been previously used in bladder cancer populations. The *primary endpoint* is the physical functioning domain score of the EORTC QLQ-C30 at 12-months.

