## 4. Data Analyses

We will use descriptive statistics to characterize the treatments received, PROs, and clinical outcomes. Prior to statistical analysis, we will first compare continuous demographic and clinical characteristics by treatment group with Wilcoxon rank-sum tests to protect against violations of normality assumptions. P-values from Exact Conditional Tests, such as Fisher's exact test and its multi-degree of freedom extensions, will be used to compare categorical data.

To address treatment selection bias and potential confounding by indication in the comparison of BST vs. radical cystectomy, we will utilize targeted maximum likelihood estimation (TMLE) as the primary analytic approach for causal effect estimation using observational data. Unlike approaches that focus on creating

carefully matched treatment and control groups, TMLE allows for the inclusion of all patient participants and their reported outcome measures. TMLE first uses covariate-adjusted regression models to generate an initial estimate of the treatment effect of radical cystectomy through the creation of *potential outcomes*: two predicted outcomes for each individual patient participant, under the hypothetical assumption that they had been treated with either radical cystectomy or BST. Next, as with a propensity score approach, we will estimate the probability of treatment with radical cystectomy using SuperLearner. The SuperLearner procedure selects the best weighted combination of prediction models from among candidate learners such as logistic regression, stepwise logistic regression, generalized additive models, Bayesian GLM, LASSO, random forest, gradient descent boosting, support vector machine, and the sample mean. Finally, we will use the probabilities obtained in the second step to update the initial estimate of each patient participant's pair of potential outcomes and the TMLE estimate is interpreted as the difference in outcomes if all patients had been treated with BST versus having been treated with radical cystectomy.

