## 4.1 Primary Outcome

Patient data will be analyzed according to an intention-to-treat (ITT) framework for the primary analysis, where the treatment arm is decided upon at enrollment regardless of whether that treatment was initiated. Patients that withdraw consent after enrollment and before the beginning treatment will be excluded from the ITT. Longitudinal trajectories of the effect of treatment on patient QOL over time will be modeled and characterized using standard linear mixed effects models for the primary analytic approach.

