### 5.4 Sensitivity Analysis

When missing data are suspected to be *missing not at random*, any standard analysis of the available cases is likely biased. The bias cannot be corrected since missingness depends on unobserved data and therefore cannot be empirically modelled reliably. We will therefore assess the sensitivity of inferences made from missing data by imputing missing data under both pessimistic and optimistic scenarios and repeating the TMLE algorithm to provide bounds on the statistical uncertainty. The characteristics of non-responders will be summarized, and we will present the heterogeneity of the treatment effect due to missing data.

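### The TMLE missing-outcome model uses baseline characteristics only, although the same scale is collected at months 3, 6 and 9; this may leave avoidable bias in the month-12 estimate

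*SAP*

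**What the plan says.** The primary endpoint in SAP 2 is a single time point, the "physical functioning domain score of the EORTC QLQ-C30 at 12-months". SAP 4 states that "we will utilize targeted maximum likelihood estimation (TMLE) as the primary analytic approach for causal effect estimation".

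For missing outcomes, SAP 5.3 brings into the TMLE update step a matrix of "missing data probabilities conditioned on baseline demographic and clinical characteristics". Protocol 9.3 describes the same procedure: "nonparametrically estimating the missing data mechanism to produce a matrix of missing data probabilities conditioned on baseline demographic and clinical characteristics". Neither section names a post-baseline variable, and neither says whether the baseline QLQ-C30 score counts as a baseline characteristic. SAP 5.3 limits its own claim accordingly: "TMLE can reduce this bias when missingness is a function of measured baseline demographic and clinical characteristics".

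Protocol Table 1 schedules the QLQ-C30 at baseline and months 3, 6, 9 and 12. Protocol 6.6 has coordinators abstract pathology, cystectomy and adverse events from the medical record during follow-up.

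Three other provisions bear on the point. SAP 4.1 has QOL trajectories "modeled and characterized using standard linear mixed effects models for the primary analytic approach". SAP 5.4 plans "imputing missing data under both pessimistic and optimistic scenarios and repeating the TMLE algorithm". SAP 4.4 imputes the floor of each instrument after death, as a sensitivity analysis.

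**The concern.** The variables most likely to predict both the month-12 score and whether it is returned are measured after baseline: the month-9 score, and events such as recurrence, complications or a later cystectomy. Missingness that depends on an observed month-9 score is missing at random given the full record, so it can be corrected. Given baseline variables alone it is not, and the stated model treats it as if it were.

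The documents make such missingness plausible without establishing it. For the Aim 2 analysis, Protocol 9.2 expects that those who survive and complete the 12-month assessment may not represent all who enrolled, and plans inverse probability weighting there. Protocol 9.1 allows for up to 20% of medical-management patients having a cystectomy within 12 months. The adverse-event profiles listed in Protocol 10.1 differ by treatment. An identical missingness process in the two arms therefore cannot be presumed.

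The direction matters. If poor function leads to missed surveys more strongly after surgery, the observed cystectomy scores are too favourable. The estimate then moves towards no difference, against the worse quality of life that Hypothesis 1.1 predicts.

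**Working it through.** **Inputs from the documents.** Effect size d = 0.24, equal to 5.5 points; 10% missing; correlation of repeated measures 0.3 (SAP 6). Planned arms of 235 and 337; two-sided alpha 0.05; power 0.80 (Protocol 9.4).

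**Reproducing the plan's figure.** Use a baseline-adjusted variance factor of 1 − 0.3² = 0.91 and allocation ratio 337/235 = 1.434.

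- Smaller arm: (1.960 + 0.842)² × 0.91 × (1 + 1/1.434) / 0.24² ≈ 210.5, so 211.
- Larger arm: 211 × 1.434 ≈ 303. Evaluable total 514.
- Enrolled: 514 / 0.9 = 571.1, so 572, which matches.

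The implied SD is 5.5 / 0.24 = 22.9 points. The standard error of the arm difference is 22.9 × √0.91 × √(1/211.5 + 1/303.3) = 1.96 points. Power is Φ(5.5/1.96 − 1.96) = 0.80. The concern does not affect the sample size.

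**Simulation.** Scores at months 0, 3, 6, 9 and 12 are multivariate normal. Missingness at month 12 is logistic in the month-9 score, with lower scores more likely to be missing. Each arm's month-12 mean is estimated by outcome regression on the baseline score alone, or on months 0 to 9. This regression stands in for TMLE, which was not run. Missing rates by arm, logit slopes (per SD), correlations above 0.3 and the AR(1) structure are assumptions. Bias is in points; a positive value flatters the first arm, taken here as cystectomy.

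| Correlation | Missing (arm 1 / arm 2) | Slope (arm 1 / arm 2) | Baseline only | Months 0–9 |
|---|---|---|---|---|
| Exchangeable 0.3 | 10% / 10% | 1 / 1 | 0.03 | 0.03 |
| Exchangeable 0.3 | 15% / 6.5% | 1 / 1 | 0.37 | 0.02 |
| Exchangeable 0.3 | 15% / 6.5% | 2 / 2 | 0.50 | 0.00 |
| Exchangeable 0.3 | 10% / 10% | 2 / 0 | 0.69 | −0.01 |
| Exchangeable 0.3 | 20% / 20% | 2 / 0 | 1.28 | 0.00 |
| AR(1) 0.7 | 15% / 6.5% | 1 / 1 | 1.05 | 0.01 |
| AR(1) 0.7 | 10% / 10% | 2 / 0 | 2.05 | 0.01 |
| AR(1) 0.85 | 30% / 10% | 2 / 2 | 3.23 | 0.01 |
| AR(1) 0.7 | 20% / 20% | 2 / 0 | 3.78 | −0.02 |

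Repeat runs at correlation 0.3 and about 10% missing gave about 0.3 to 0.6, hence the range of 0.3 to 0.7 used here.

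**Hand check.** The bias in one arm is approximately the slope of month 12 on month 9 given baseline, times the part of the month-9 shift among responders that baseline does not explain. With 10% missing and slope 2, responders' month-9 mean is 0.143 SD too high.

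- Exchangeable 0.3: slope 0.3/1.3 = 0.231; unexplained shift 0.91 × 0.143 = 0.130; bias 0.231 × 0.130 × 22.9 = 0.69 points.
- AR(1) 0.7: slope 0.7; unexplained shift (1 − 0.343²) × 0.143 = 0.126; bias 0.7 × 0.126 × 22.9 = 2.0 points.

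Both agree with the simulation. The result therefore depends mainly on how much better month 9 predicts month 12 than baseline does.

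**Consequence.** At 0.69 points the bias is 0.69/5.5 = 13% of the target and 0.69/1.96 = 0.35 standard errors. Directed towards no difference, it lowers power at a true 5.5 points to Φ((5.5 − 0.69)/1.96 − 1.96) ≈ 0.69. A 0.7-point bias lowers 95% interval coverage to about 93.5%.

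**The case against.** The strongest reply is that the bias is assumed. The documents give no missing rate by arm and no link between month-9 function and non-response, and with the same rate and mechanism in both arms the bias is nil. On the plan's own inputs it is at most about a third of a standard error. Both points stand. A reader might infer that the primary estimate is biased; the documents support only that it may be.

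A reader might also infer that the interim scores are ignored throughout the plan. They are not: the mixed model in SAP 4.1 would use them. But SAP 4 assigns control of confounding by indication to TMLE. The mixed model has no stated confounder set or month-12 contrast, and the SAP does not say which of the two approaches called primary gives the month-12 estimate. It does not repair the TMLE.

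The scenarios in SAP 5.4 are undefined and bound the result without changing the point estimate. They also address missingness that the SAP itself calls uncorrectable, whereas dependence on recorded scores is correctable. Floor imputation covers deaths only. The priority that SAP 5.1 gives to outcome measures in a shortened assessment may reduce missingness, but does not adjust for what remains.

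Nor do the near-zero values in the last column promise complete removal. They assume that everyone missing month 12 was seen at month 9. In a check with 10% missing per arm, slopes 1.5 and 0, correlation 0.3 and month 9 as the only interim visit, baseline-only bias was about 0.57. When 80% of those missing month 12 had also missed month 9, about 0.43 remained. Months 3 and 6 could recover part of that.

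Finally, SAP version 1.0 carries the date of the first data freeze, so any change now follows that freeze. This is a fair reason for disclosure, and for keeping the stated analysis in view.

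**Conclusion.** The point holds in conditional form. The stated TMLE missingness model omits the interim measurements of the endpoint's own scale, and may leave avoidable bias in the month-12 estimate if non-response depends on interim function and differs between arms in rate or mechanism.

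The size is about 0 when the arms behave alike, and about 0.3 to 0.7 points at the plan's correlation and 10% missing. Values of roughly 1 to 3 points, with 3.8 in the harshest case run, need assumptions that the plan does not make: 20% to 30% missing in an arm, or AR(1) correlation of 0.7 to 0.85 between adjacent visits together with a difference between arms. The figures rest on normal scores, logistic dependence on month 9, and outcome regression in place of TMLE.

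This is a worthwhile and inexpensive improvement to the primary analysis. It does not show that the planned result would be wrong.

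**What to change.** Before the final data set is analysed (SAP 1.6 estimates January 2025), amend SAP 5.3 and Protocol 9.3:

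- Handle missing month-12 outcomes using physical functioning at months 3, 6 and 9 and recorded post-baseline events: recurrence or progression, cystectomy after bladder-sparing therapy, and hospitalisation.
- Do this by sequential-regression (longitudinal) TMLE with a missingness model at each visit, or by multiple imputation within arm followed by TMLE.
- State that the baseline QLQ-C30 score is included.
- Use the post-treatment variables only in the missingness and sequential outcome models, or in the imputation model. They must not enter the confounder set, where they would adjust away part of the treatment effect.
- State in SAP 4 and 4.1 that this TMLE gives the month-12 estimate, and what the mixed model is for.
- Report the baseline-only TMLE alongside, and disclose that the change was made after the March 14, 2024 freeze.

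No new data or visits are needed. The cost is additional programming, and possibly more variance if weights become extreme. Bias would be only partly removed for patients who had already dropped out by month 9, so the SAP 5.4 scenarios should stay.
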